4. STUDY POPULATION

4.1. Inclusion criteria

- woman
- age ≥ 70 years
- recurrent UTIs defined as ≥ 3 episodes of antibiotic treated acute cystitis (acute symptoms specific/related to the urinary tract) during the last twelve months or ≥ 2 episodes during the last 6 months
- able and willing to comply with all trial requirements
- able and willing to give informed consent.

4.2. Exclusion criteria

- the patient has taken methenamine hippurate within the last 12 months
- the patient is allergic to methenamine hippurate
- the patient is having current antibiotic prophylaxis for UTI

- the patient has a urinary catheter (chronic indwelling catheters as well as intermittent urinary catheterisation)
- the patient has known severe chronic renal failure or estimated creatinine glomerular filtration rate ≤ 30 ml/min (known = registered in GP' clinical records)
- the patient has a known condition or treatment associated with significant impaired immunity (e.g. long-term oral steroids, chemotherapy, or immune disorder) (known = registered in GP clinical records)
- the patient has a known severe hepatic impairment (known = registered in GP clinical records)
- the patient is suffering from severe dehydration
- the patient has shown signs of gout
- the patient has a need for long term use of antacids such as magnesium hydroxide, magnesium carbonate, aluminium hydroxide
- the patient has a life expectancy estimated by a clinician to be less than six months
- the patient has been involved in, including completion of, follow-up procedures, in another clinical trial of an investigational medicinal product in the last 90 days
- the patient suffers from incontinence too severe to be able to provide a voided urine specimen
- the patient is participating in ImpresU Work Package 2
- the patient is suffering from significant known abnormal renal tract anatomy/physiology (i.e. single kidney, persistent urinary tract stone disease, severe vesicoureteral reflux) or neuropathic bladder disorders
- the patient has lactose intolerance.

4.3. Subject enrolment and randomization

Included participants will be randomised strictly sequentially, as subjects are eligible for randomisation. If a subject discontinues from the study, the subject number will not be re-used, and the subject will not be allowed to re-enter the study.

Four sets of 100 random numbers each, one for each participating country, will be created using Research Randomizer. A block randomisation will be performed (the block size is concealed to prevent functional unblinding). The outcome will be transferred to a separate Excel spreadsheet for each country where each row, representing one patient, is sequentially numbered. Norway will have the numbers 1-100, Sweden 101-200, the Netherlands 201-300 and Poland 301-400. Each country will follow their randomisation list strictly sequentially. The inclusion will stop when a total of 400 participants are included in the study.

4.4. Discontinuation and withdrawal of subjects

4.4.1. Withdrawal of subjects

Subjects are free to discontinue their participation in the study at any time without prejudice to further treatment. In either case, serious adverse events where relation to IMP cannot be excluded, will be followed up. Other reasons for discontinuing a subject are incorrect enrolment and subjects lost to follow-up.

Any subject fulfilling any of the pre-defined exclusion criteria will be withdrawn from the study:

- participating patients withdrawing their consent, subjects are free to discontinue their participation in the study at any time without prejudice to further treatment
- participating patients developing allergic reactions or any other SAE possibly due to methenamine hippurate
- participating patients requiring long term use of alkalinizing substances (such as antacids) during the first six months when taking IMP as alkalinizing substances reduces the effect of methenamine hippurate and should be avoided
- participating patients developing serious illness making it impossible for them to continue taking the study tablets.

Simultaneous intake of sulphonamide antibiotics can increase risk of crystalluria. Therefore, methenamine hippurate will temporarily be paused if the participant is prescribed a course of sulphonamide antibiotics, but will continue with IMP after that.

Participating patients developing clinically significant dehydration will not receive IMP until clinically resolved dehydration, but will continue with IMP after that.

Those patients who have to prematurely stop taking the IMP, except for patients' withdrawing their consent, will be followed up in the same framework of the study and in the same way as participants receiving IMP.

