3.3. Table 1. Study visits

Day(s)	Visit 1 Screening and randomisation	Telephone follow-up in case of acute UTI episode(s)	Telephone follow-up every 30 days in all patients	Telephone contact by end of treatment	Telephone contact by end of study
	1	2-360	2-180	180	360
Informed consent	X				
Demography, level of care	X				
Medical history	X				
Physical examination***	X				
Dipstick urinalysis and urine culture	X	X			
Inclusion/exclusion criteria	X				
Randomisation	X				
Patient Reported Outcome		X	X	X	X
Concomitant medication**	X				
Serious Adverse Events		X	X	X	X*

* In case of SAE present and not resolved by day 360, this will be followed until resolution.

** After visit 1 concomitant medication will only be registered in case of SAE, otherwise not.

*** If needed to determine eligibility or complete baseline data.

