If the patient presents with symptoms of an acute UTI or are on antibiotic treatment for a UTI at the inclusion visit, the infection is handled by regular health services (GP or out of Hours (OOH) service). The patient will wait until 2 weeks after finishing treatment for the UTI before the researcher completes the inclusion and takes the baseline urine sample. The treatment with IMP will start the day after the completed inclusion of the patient. The current UTI should be registered at the baseline form as a UTI prior to inclusion in the study. The same procedure will be followed if the patient is on prophylactic treatment with UTI antibiotics, but is willing to stop the prophylactic treatment to enter the study. A note of the actions taken will be written in the comments section in the baseline CRF by the responsible researcher.

All data related to inclusion visit including trial name, study-ID and informed consent will be documented in the medical record of the patient.

Telephone follow-up in case of acute UTI episode(s)

Any episodes of acute UTI during the follow-up period (day 2-360) will be handled by regular health services (GP or out of Hours (OOH) service). Participants are informed at inclusion (Visit 1) to contact the trial team in case of any UTI-related health care contacts during the follow-up period. The study team will follow up each UTI episode until resolved with registration of relevant data by telephone contact and by ordering copies of medical records regarding the UTI episode including laboratory results regarding urinary dipsticks and urine culture.

Following data will be collected in case of acute UTI episode(s) during day 2-360 (telephone follow-up and from medical record):

- confirmation and registration of UTI symptoms (acute symptoms specific/related to the urinary tract), registration of symptom severity when initiating treatment for UTI. This will be measured by a scale 0-6 (no symptoms to worst possible) for each of the three cardinal

symptoms and general condition, Patient Reported Outcome (PRO) – grading of symptoms, see appendix

- UTI antibiotic treatment (name of drug, dosage and duration)
- registration of any pyelonephritis and hospital admission for UTI
- ordering copies of medical records regarding the UTI episode including laboratory tests performed by regular health service (dipstick urinalysis regarding nitrite and leukocyte esterase and urine culture)

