- SAEs, whereas relationship with IMP cannot be excluded.

In case of an episode of UTI all clinically relevant data have already been recorded in the patient's medical record by the physician, therefore these telephone follow-ups will only be recorded in the CRF. In case of SAE this will be recorded in the medical record.

Telephone contacts every 30 days during the first six months as well as day 360

During telephone contacts every 30 days during the first six months as well as day 360 registration of any symptoms and side effects from the trial medication will be recorded as well as SAEs, whereas relationship with IMP cannot be excluded. Participants will be asked if they have forgotten to contact the study team in case of any UTI-related health care contacts. If so, the study team will follow up these UTI episode(s) with registration of relevant data as described above.

In case of new UTI not recorded, we will record PRO using the scale. In case of an episode of UTI all clinically relevant data have already been recorded in the patient's medical record by the physician, therefore these telephone follow-ups will only be recorded in the CRF. In case of SAE this will be recorded in the medical record. By the end of the project period, the study team will contact the patients' GP, and ask the GP to go through the patients' records during the project period in order to validate the number of UTI episodes.

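### Protocol 4.4.1 withdraws from the study women whom it also says to follow up, and does not clearly keep wrongly enrolled randomised women in follow-up

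*Protocol*

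**What the plan says.** Protocol 4.4.1 contains three statements about who leaves and who stays.

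- The lead-in to the list: "Any subject fulfilling any of the pre-defined exclusion criteria will be withdrawn from the study". Four cases follow: withdrawn consent; allergy or another SAE possibly due to methenamine hippurate; a need for long-term alkalinizing substances during the treatment period; and serious illness that makes taking the tablets impossible.
- The paragraph before it: "Other reasons for discontinuing a subject are incorrect enrolment and subjects lost to follow-up".
- The closing sentence: women who have to stop IMP early, apart from those withdrawing consent, "will be followed up in the same framework of the study and in the same way as participants receiving IMP".

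Sections 5.4 and 7.1 say again that women who come to need long-term alkalinizing substances are withdrawn, and neither mentions follow-up. Section 4.3 bars a subject who has discontinued from re-entering.

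SAP 5.1.1 defines the primary ITT analysis as all randomised women with a full set of baseline observations. It has no exclusion for ineligibility.

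**The concern.** The lead-in and the closing sentence give opposite instructions for the same women. Consent withdrawal is the only listed case that the closing sentence exempts, so the other three are both withdrawn from the study and kept in it.

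For a wrongly enrolled woman the text is less clear still. She is named, beside women lost to follow-up, as someone to discontinue. The closing sentence reaches her only if she is read as someone who has to stop IMP. Yet she was randomised and belongs to the ITT set if her baseline data are complete.

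What is at stake is data collection after randomisation in women who have not withdrawn consent. If a site applies the withdrawal wording, their remaining counts are no longer observed and must be constructed. Sites in four countries have to apply this paragraph, and the re-entry bar in 4.3 makes a mistaken withdrawal hard to reverse.

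**Working it through.** **1. The two rules side by side**

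| Case in Protocol 4.4.1 | Withdrawal wording | Closing sentence |
|---|---|---|
| Consent withdrawn | leaves the study | exempted, so consistent |
| Allergy or SAE possibly due to the drug | leaves the study | followed up: conflict |
| Long-term alkalinizing substances | leaves the study (5.4 and 7.1 also say withdrawn) | followed up: conflict |
| Illness preventing tablet intake | leaves the study | followed up: conflict |
| Incorrect enrolment | discontinued | covered only if she is read as having to stop IMP |

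**2. What happens to the data if the withdrawal wording is applied**

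- *Six-month counts.* Under SAP 5.1.1, a woman leaving after at least three but less than six months has her count extrapolated to six months. One leaving before three months receives the mean of same-arm women within five years of her age.
- *Severity and duration (2c, 2d).* Protocol 3.4: "The study team will follow up each UTI episode until resolved with registration of relevant data by telephone contact". Section 9.1.1 names the CRF as the source document for symptom severity. These data therefore depend on contact with the study team.
- *Scheduled contacts.* Table 1 has "Telephone follow-up every 30 days in all patients" for days 2-180, plus contacts at days 180 and 360. Counting day 180 once gives days 30, 60, 90, 120, 150, 180 and 360, which is 7 calls. A woman withdrawn at day 90 misses days 120, 150, 180 and 360, which is 4 of 7.

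**3. Possible size for the primary estimate**

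The planned effect comes first. Protocol 8.1 assumes six-month means of 2.0 (placebo) and 1.5 (active), so the ratio is 1.5/2.0 = 0.750, the stated 25% reduction.

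Assumptions, none of them in the documents: a share w of each arm meets a listed stop, with w from 2% to 10% (4 to 20 of 200). Stopping times are spread evenly over the six months and are unrelated to the woman's earlier rate. On average, half of the period then remains after the stop.

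- *Withdrawn and handled as in SAP 5.1.1:* expected means stay at 2.0 and 1.5, so the ratio is 0.750.
- *Followed:* arm mean = m + w × 0.5 × (six-month rate after stopping − m), where m is the planned mean.
  - Drug effect kept after stopping: ratio 0.750.
  - Drug effect lost: the active mean is 1.5 + w × 0.5 × (2.0 − 1.5) = 1.5 + 0.25w, and the placebo mean stays at 2.0.
    - w = 2%: 1.505/2.0 = 0.7525
    - w = 5%: 1.5125/2.0 = 0.756
    - w = 10%: 1.525/2.0 = 0.7625

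The largest shift in this range is 0.7625 − 0.750 = 0.0125 on the ratio scale. These cases do not establish a direction. If the arms stop at different rates, or the illness behind the stop changes the UTI rate, the shift could be larger or go the other way.

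**The case against.** The strongest reply is that 4.4.1 answers its own question. The closing sentence is the only one that says what happens after IMP is stopped, and its single exception removes exactly one of the four listed cases. Section 7.3.1 likewise speaks of removal from treatment, not from the study. A careful site would follow all three IMP-stop cases, which is the design asked for here. This largely stands: for those cases the intent is clear and the fault lies in the lead-in. It does not stand for wrongly enrolled women, where no sentence clearly states the intent.

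Data loss would also be partial. At the end of the project the GP is asked to go through the patients' "records during the project period in order to validate the number of UTI episodes". Pyelonephritis and admissions are taken from medical records as well as by telephone, and 4.4.1 keeps SAEs possibly related to IMP in follow-up. That stands for numbers of episodes and complications, provided the record review extends to withdrawn women, which 3.4 does not say. It does not recover symptom severity, or duration followed to resolution.

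A reader might infer more than the documents support:

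- *That the lead-in contradicts the dehydration rule.* Section 4.2 excludes a woman if "the patient is suffering from severe dehydration", while under 4.4.1 a participant with clinically significant dehydration "will not receive IMP until clinically resolved dehydration, but will continue with IMP after that". This is not a working conflict. The lead-in runs into a list that omits dehydration, and 4.4.1 and 5.4 both give a specific rule to pause IMP.
- *That objective 2a is pulled towards no difference.* Protocol 8.2 gives women who leave before the second period one median for both groups. SAP 5.1.1 rewrites the missing-data rules without repeating this, so its status is unclear and no figure can rest on it.

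**Conclusion.** The point holds as an inconsistency in the follow-up rules that should be corrected. Its strongest part is incorrect enrolment, where a randomised woman can be discontinued and no sentence clearly keeps her in follow-up. For the three IMP-stop cases the wording conflicts with an intent that the same section makes clear.

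The documents do not say how many women would be affected. Under the assumptions above (2-10% stopping in each arm, even timing, stopping unrelated to earlier rate), the primary ratio is 0.750 with withdrawal and 0.750 to 0.763 with follow-up. The effect is probably small and its direction unknown. A reader might infer that the primary result is biased in favour of the drug. The documents do not support that, because they give neither the stopping rates by arm nor the UTI rates after stopping. A reader might also infer that the analysis drops ineligible women. It does not: SAP 5.1.1 has no such exclusion, so the problem is the collection of data and not the analysis set. The gain from correction is fewer constructed counts and more complete severity, duration and later follow-up data.

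**What to change.** - In Protocol 4.4.1, 5.4 and 7.1, replace the withdrawal wording with *stop IMP* for every case other than withdrawn consent.
- In 4.4.1, add a sentence to this effect: every randomised woman who has not withdrawn consent, including one found to have been wrongly enrolled, is followed to day 360 and analysed as randomised.
- Leave the clinical rules for stopping or pausing IMP as they are. The sample size does not change.

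The cost is a wording change in three sections, at most seven scheduled calls per woman kept in follow-up, and the calls for her UTI episodes.

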4.4.2. Premature termination of the study

The difference between groups in SAEs deemed to be linked to methenamine hippurate will be continuously monitored (appendix 5). The study will be terminated if there is a significant difference between the two trial arms regarding SAE, SAR and SUSAR probably or definitely related to the trial medication or UTI. This will be done by comparing the two groups without breaking the code. The code will be broken if the difference between groups in these adverse effects are statistically significant ($p<0.05$). The study will be prematurely terminated if the statistical difference is to the disadvantage of active IMP. SAE, SAR and SUSAR possibly related to the trial medication or UTI will be registered but not used for decision making for eventual premature termination of the study. The investigator will promptly inform the participants, the Ethics Committee (EC) and other relevant regulatory authorities according to national regulations providing a detailed written explanation.

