- able and willing to comply with all trial requirements
- able and willing to give informed consent

Exclusion criteria:

- the patient has taken methenamine hippurate within the last 12 months
- the patient is allergic to methenamine hippurate
- the patient is having current antibiotic prophylaxis for UTI
- the patient has a urinary catheter (chronic indwelling catheters as well as intermittent urinary catheterisation)
- the patient has known severe chronic renal failure or estimated creatinine glomerular filtration rate ≤ 30 ml/min (known = registered in GP clinical records)
- the patient has a known condition or treatment associated with significant impaired immunity (e.g. long-term oral steroids, chemotherapy, or immune disorder) (known = registered in GP clinical records)
- the patient has a known severe hepatic impairment (known = registered in GP clinical records)
- the patient is suffering from severe dehydration
- the patient has gout
- the patient has a need for long term use of antacids such as magnesium hydroxide, magnesium carbonate, aluminium hydroxide
- the patient has a life expectancy estimated by a clinician to be less than six months
- the patient has been involved in, including completion of, follow-up procedures, in another clinical trial of an investigational medicinal product in the last 90 days
- the patient suffers from incontinence too severe to be able to provide a voided urine specimen
- the patient is participating in ImpresU Work Package 2
- the patient is suffering from significant known abnormal renal tract anatomy/physiology (i.e. single kidney, persistent urinary tract stone disease, severe vesicoureteral reflux) or neuropathic bladder disorders
- lactose intolerance.

Premature termination of the study

The difference between groups in SAEs deemed to be linked to possible treatment with methenamine hippurate will be continuously monitored without breaking the code. The study will be terminated in case there are significantly more SAEs within one of the groups during the trial.

Investigational product, dosage and administration: Methenamine hippurate 1 gram or placebo per os morning and evening day 1-180.

[figure not shown]
Primary outcome variables and examinations: Number of UTI courses during day 2-180

Study period: 1 November 2019 to 31 December 2022.

SIGNATURE PAGE

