LIST OF APPENDICES

1. Farmasøytisk/kjemisk dokumentasjon for Hiprex, Kragerø tabletproduksjon A/S.
2. SmPC Hiprex, Meda.
3. Etikettforslag norsk
4. Patient reported outcome
5. Safety reporting flow-chart
6. EMA-akkreditering
7. Mail Legemiddelansvarsforsikring
8. Legemiddelansv.forsikring Kragerø tabl.prod.

LIST OF ABBREVIATIONS

Abbreviation	Explanation
ADR	Adverse Drug Reaction
AE	Adverse Event
AMR	Antimicrobial Resistance
CA	Competent Authority
EC	Ethics Committee
(e)CRF	(electronic) Case Report Form
EDC	Electronic Data Capture
GCP	Good Clinical Practice
GP	General Practitioner
ICF	Informed Consent Form
IMP	Investigational Medicinal Product
ImpresU	Improving rational prescribing for UTI in frail elderly
ISF	Investigator Study File
OOH	Out Of Hours Service
PI	Principal Investigator
PRO	Patient Reported Outcome (PRO)
RCT	Randomised Controlled Trial
RO	Research Online
SAE	Serious Adverse Event
SAR	Serious Adverse drug Reaction
SmPC	Summary of Product Characteristics
SUSAR	Suspected Unexpected Serious Adverse Reactions
UTI	Urinary Tract Infection
WP	Work Package

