1.3. Risk/Benefit evaluation

Potential benefits from IMP:

- decreased total use of UTI antibiotics
- reduced antibiotic pressure on gut microbiota in the population and possibly reduced antimicrobial resistance (AMR) in the population
- decreased number of UTIs
- increased quality of life.

Potential risks from IMP:

- polypharmacy, many patients have a large number of regular medication, and methenamine hippurate will be a new one for six months
- simultaneous intake of sulphonamide antibiotics can increase risk of crystalluria. Therefore methenamine hippurate will temporarily be paused if the participant gets a course of sulphonamide antibiotics. There are no other known clinical relevant interactions between methenamine hippurate and other pharmaceuticals.

Anticipated adverse drug reactions in the study:

Methenamine hippurate is well tolerated and adverse effects are rare and generally mild (10). Possible side effects might be minor gastrointestinal upsets, dysuria (seldom), abdominal cramps, anorexia, rash and stomatitis (10). The trial team will be available on telephone for urgent cases during the whole study period. This will be solved for each country.

Risk/benefit rationale:

- The benefit of the study is potentially great for elderly women with recurrent UTI resulting in fewer UTI episodes, reduced antibiotic usage and therefore also reducing the risk of AMR.
- The risk of the study is considered to be very small.

In summary the benefits greatly outweigh the potential small risks. This will be evaluated and confirmed by relevant ECs before commencing the trial.

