2. STUDY OBJECTIVES AND ENDPOINTS

The primary objective of this study is to investigate if taking methenamine hippurate reduce the need for antibiotic usage due to recurrent UTI (measured as number of antibiotic courses). The remaining objectives are considered secondary. Pyelonephritis, hospitalization and death will be registered as safety endpoints in the study.

Objectives	Outcome Measures / variables / endpoints	Time point(s) of evaluation of this outcome measure (if applicable)
Primary Objective		
1 The primary objective of this study is to investigate if taking methenamine hippurate reduces the need for antibiotic usage due to recurrent UTI (measured as number of antibiotic courses).	Number of UTI antibiotic treatments during the six months of treatment. If the participant receives >1 antibiotic course for UTI without symptom relief it is regarded as one episode and counted as one antibiotic treatment. If there has been an asymptomatic period of at least 14 days in-between two UTI antibiotic	After six months of treatment.

		courses, this is regarded as a new antibiotic treatment.	
Secondary Objectives			
2a	To investigate if methenamine hippurate will have a prolonged effect on antibiotic usage even after discontinuation.	Number of UTI antibiotic treatments during the six months following completion of treatment. If the participant receives >1 antibiotic course for UTI without symptom relief it is regarded as one episode and counted as one antibiotic treatment. If there has been an asymptomatic period of at least 14 days in-between two UTI antibiotic courses, this is regarded as a new antibiotic treatment.	Six months after completing (12 months after commencing) treatment.
2b	To investigate if taking methenamine hippurate reduces the incidence of UTI.	Number of UTIs (acute symptoms specific/related to the urinary tract) during the six months of treatment. If the participant has had >1 UTI episode without symptom relief it is regarded as one episode. If there has been an asymptomatic period of at least 14 days in-between two UTI episodes, this is regarded as a new episode.	After six months of treatment.
2c	To investigate if methenamine hippurate can reduce severity of UTI symptoms.	Registration of symptom severity when initiating treatment for UTI.	After six months of treatment.

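### The only p<0.05 safety stopping rule pools drug-related with UTI-related serious events, so it can miss an excess in the drug-related events that the protocol says it monitors

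*Protocol*

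**What the plan says.** Section 4.4.2 of the protocol opens by stating that between-arm differences in SAEs attributed to the drug are watched continuously, and points to appendix 5 ("Safety reporting flow-chart"). The synopsis describes the same target: "The difference between groups in SAEs deemed to be linked to possible treatment with methenamine hippurate will be continuously monitored without breaking the code". Its next sentence adds: "The study will be terminated in case there are significantly more SAEs within one of the groups during the trial". That sentence gives no p-value and does not itself say which SAEs count.

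The rule with a threshold is in 4.4.2. It looks for a "significant difference between the two trial arms regarding SAE, SAR and SUSAR probably or definitely related to the trial medication or UTI". The code is broken at p<0.05, and the trial stops if the difference is against active treatment. Events only possibly related to the drug or to UTI "will be registered but not used for decision making for eventual premature termination of the study".

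UTI-related SAEs such as pyelonephritis must be reported under 7.3.3, so they enter this count. Section 2 states: "Pyelonephritis, hospitalization and death will be registered as safety endpoints in the study". The same section lists UTI complications as efficacy objective 2e. The committee in 10.3 meets every six months, has no boundary of its own, and refers back to the termination rule. The SAP contains no safety stopping rule.

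**The concern.** The events said to be monitored and the events that trigger action are different sets. A reader of the opening sentence of 4.4.2 would expect a significant excess of drug-related SAEs on active to break the code. Under the rule as written, that excess is tested only after UTI-related SAEs have been added.

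All participants have recurrent UTI, so some UTI-related SAEs are to be expected in both arms, and they dilute a drug-related difference. If the drug also lowers UTI complications, as objective 2e allows, the UTI component favours active and offsets drug harm directly. At stake is a drug-related difference that meets the protocol's own p<0.05 criterion and yet leads to neither a code break nor a stop.

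**Working it through.** **No figure to reproduce.** The documents state no SAE rate, test, sidedness, number of looks or operating characteristic for this rule. The arm size of 200 comes from protocol 5.1 (200 active and 200 placebo sets), and the 0.05 threshold and the direction rule from 4.4.2. The rest is assumed: a two-sided Fisher exact test, firing only if active has more events.

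**Worked counts, 200 per arm.**
- Drug-related 6 v 0: p = 2 × C(200,6)/C(400,6) = 2 × 0.01504 = 0.030. The rule fires. At 5 v 0, p = 0.061.
- Add one UTI-related SAE per arm: 7 v 1, p = 0.068. Silent.
- Add two per arm: 8 v 2, p = 0.105. Silent.
- Add 6 active and 8 placebo (some UTI benefit): 12 v 8, p = 0.49. Silent.

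**Probabilities.** Each woman counts once. With drug-related rate d and UTI-related rate u, taken as independent, the combined rate is 1 − (1−d)(1−u). For d = 4% v 0.5% and u = 2% in both arms, this is 1 − 0.96×0.98 = 5.92% against 1 − 0.995×0.98 = 2.49%. Exact binomial sums over the Fisher test at one look, with no UTI benefit, give the table below. *Missed* means that drug-related events alone reach p<0.05 while the combined rule is silent.

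| UTI-SAE rate, both arms | 0.25% | 0.5% | 1% | 2% | 4% | 10% |
|---|---|---|---|---|---|---|
| **Drug 4% v 0.5%** (drug-only fires 56%): combined fires | 51% | 46% | 39% | 31% | 22% | 13% |
| missed | 9% | 14% | 21% | 29% | 38% | 46% |
| **Drug 2% v 0** (drug-only 21%): combined fires | 21% | 19% | 17% | 13% | 10% | 6% |
| missed | 6% | 9% | 12% | 15% | 17% | 19% |
| **Drug 1% v 0** (drug-only 1.6%): combined fires | 2.6% | 3.4% | 4.3% | 4.4% | 4.1% | 3.4% |

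At 1.5% v 0, drug-only fires in 8%, combined in 5 to 10%, and 3 to 7% are missed.

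**With a UTI benefit.** If the drug cuts UTI-related SAEs by 25%, the active UTI rate is 0.75u. At d = 4% v 0.5% the combined rule fires in 24% for a placebo UTI-SAE rate of 2%, and in 13% for 4%, against 56% for drug-only.

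**Both triggers together.** Over the UTI-SAE rates in the table, at least one fires in 59 to 61% of trials at 4% v 0.5%, and in 25 to 29% at 2% v 0. If both components are worse on active (drug 2% v 0, UTI 4% v 2%), drug-only fires in 21%, combined in 43%, and either in 49%.

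**Repeated looks.** With four assumed looks at 50, 100, 150 and 200 per arm (300,000 simulated trials) and drug 4% v 0.5%, drug-only fires in 58%, combined in 54% down to 18%, and either in 62 to 63%.

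**False alarms.** The largest increase found was with 2% drug-related and 10% UTI-related SAEs in both arms: 1.74% to 2.49% at one look (0.75 points), and 3.9% to 4.9% at four looks (1.0 point). It stays at about 1 point with twenty looks. With 0.5% drug-related SAEs in both arms, the one-look increase is 0.01 to 0.02 points.

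**The case against.** **The synopsis may already contain a drug-linked stop.** A reader might infer that drug-related events have no between-arm rule anywhere in the protocol. The documents do not support that. The two synopsis sentences, read together, can be taken as a stop for significantly more drug-linked SAEs. What stands is narrower: that sentence sets no p-value, and the only p<0.05 rule is the combined one.

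**The wording of 4.4.2 could mean separate comparisons.** It lists SAE, SAR and SUSAR, and under 7.3.3 the last two are drug-related classes. A class-by-class reading is possible but less natural, and no separate test is stated. Appendix 5, which is cited for the monitoring, was not available and may hold one.

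**Counting UTI events is sensible.** A reader might infer that they should be removed from the rule. They should not: pyelonephritis and hospitalisation are declared safety endpoints, and the combined count detects net harm better, as the 43% against 21% shows.

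**The rates are assumed and may be too high.** Section 1.3 expects adverse effects to be rare and mild. At 1% v 0 or below, neither rule has useful power, and without a UTI benefit the combined rule is the more sensitive. This stands and limits the weight of the point.

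**Other safeguards exist.** Individual withdrawal, SUSAR reporting, the annual safety report and the committee's meetings all operate, so it would be wrong to infer that drug harm would go unseen. In the supplied text, though, they act on single cases or overall safety, and none sets a significance criterion for a between-arm drug-related difference.

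**Conclusion.** The concern holds as a minor gap between what 4.4.2 and the synopsis say is monitored and what the p<0.05 rule counts. On the natural reading, a drug-related excess that is significant by itself can fail to break the code once UTI-related SAEs are added. One such event per arm is enough to turn 6 v 0 into a non-significant result.

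The direction follows from the pooling. The size rests on assumed rates: from about 1% of trials missed at 1% v 0 to 46% at 4% v 0.5% with a 10% UTI-SAE rate. It also assumes Fisher's test, 200 per arm, independence of the two event types and, except where stated, no UTI benefit. Confidence is moderate because the wording of 4.4.2 allows another reading and appendix 5 could not be checked.

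**What to change.** Keep the combined trigger. Add to 4.4.2 a separate between-arm comparison of SAE, SAR and SUSAR judged probably or definitely related to the trial medication, with the same p<0.05 and direction rule. Name Fisher's exact test and tie the evaluation to the committee's six-monthly meetings. Align the synopsis termination sentence with this, and give the committee drug-related and UTI-related SAEs in separate rows by coded arm. If appendix 5 already contains the comparison, stating it in 4.4.2 is enough.

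The cost is protocol wording plus recording a judgement that 7.3.3 already assigns to the national principal investigators; whether the SAE form has a field for it cannot be seen from the documents. The price is the small rise in false alarms shown above. The gain is confined to larger drug-related differences: at 1% v 0 or below, the added trigger contributes almost nothing.
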